3. STUDY OBJECTIVES

3.1. Primary Objective

The primary objectives of Phase 1 dose escalation/Part 1 Expansion are:

- To assess the safety and tolerability of treatment with AG-221 administered continuously as a single agent dosed orally on Days 1 to 28 of a 28-day cycle in subjects with advanced hematologic malignancies.
- To determine the maximum tolerated dose (MTD) or maximum administered dose (MAD) and/or the recommended Phase 2 dose (RP2D) of AG-221 in subjects with advanced hematologic malignancies.

The primary objective of Phase 2 is:

- To assess the efficacy of AG-221 as treatment for subjects with relapsed or refractory (R/R) acute myelogenous leukemia (AML) with an isocitrate dehydrogenase-2 (IDH2) mutation.

3.2. Secondary Objectives

The secondary objectives of Phase 1 dose escalation/Part 1 Expansion are:

- To describe the dose limiting toxicities (DLTs) of AG-221 in subjects with advanced hematologic malignancies.
- To characterize the pharmacokinetics (PK) of AG-221 and its metabolite in subjects with advanced hematologic malignancies.
- To characterize the PK/pharmacodynamic (PD) relationship of AG-221 and 2-hydroxygluturate (2-HG).
- To characterize the clinical activity associated with AG-221 in subjects with advanced hematologic malignancies.

The secondary objectives of Phase 2 are:

- To further evaluate the safety profile of AG-221 in subjects with R/R AML with an IDH2 mutation.
- To characterize the PK of AG-221 and its metabolite in subjects with relapsed or refractory AML with an IDH2 mutation.
- To characterize the PK/PD relationship of AG-221 and 2-HG.

4. INVESTIGATIONAL PLAN

4.1. Overall Study Design and Plan

This is a Phase 1/2, multicenter, open-label, 3-part (Phase 1 dose escalation, Part 1 Expansion, and Phase 2), safety, PK/PD, and clinical activity evaluation of orally administered AG-221 in subjects with advanced hematologic malignancies with an IDH2 mutation. The study includes a dose escalation phase to determine MTD /MAD and/or RP2D; an expansion phase (Part 1 Expansion) to further evaluate the safety, tolerability, and clinical activity of AG-221; and a Phase 2 portion to assess the clinical efficacy of AG-221 at the RP2D and to further evaluate safety in subjects with R/R AML carrying an IDH2 mutation.

[figure not shown]
The dose escalation phase of the study will be conducted in up to 5 subjects per dose level; with the exception that the MTD/MAD requires 6 subjects. Additional subjects may be needed during dose escalation (for the replacement of subjects who are not evaluable for PK/PD, safety, clinical activity and for evaluation of alternative dosing regimens other than the planned escalation scheme or the MTD/MAD) to optimize the RP2D and regimen(s).

The Part 1 Expansion will enroll 4 cohorts, each comprised of a minimum of 25 subjects in specific hematologic malignancy subsets (a minimum of 100 subjects).

The Phase 2 portion will enroll a cohort of approximately 125 subjects with R/R AML.

Additional subjects may be needed for the expansion phase for the replacement of subjects who are not evaluable for PK/PD, safety, or clinical activity, or for evaluation of alternative dosing regimens.

Figure 1: Study Diagram

[figure not shown]

Note: Part 1 Expansion and Phase 2 at 100 mg QD will proceed in parallel as soon as this dose is declared safe during the dose escalation portion of the study.

4.1.1. Overview of the Phase 1/Dose Escalation Phase

A schematic of the dose escalation scheme is provided in Figure 2. The dose escalation phase will utilize a standard “3+3” design. During the dose escalation phase, consented eligible subjects will be enrolled into sequential cohorts of increasing doses of AG-221. Each dose cohort will plan to enroll a minimum of 3 subjects. The initial dosing regimen was twice daily (BID) (approximately every 12 hours). Based on the emerging data, a once daily (QD) dosing schedule was implemented. Alternative dosing schedules (eg, loading dose followed by QD dosing) may continue to be explored in the dose escalation and expansion phases as agreed upon by the Clinical Study Team. If there are multiple subjects in the screening process at the time the third subject within a cohort begins treatment, up to 2 additional subjects may be enrolled, for a maximum of 5 subjects per cohort, with approval of the Medical Monitor.

Figure 2: Dose Escalation Scheme

* If only 3 subjects were enrolled at the MTD level, an additional 3 subjects will be enrolled to confirm that <2 of 6 subjects experience a DLT at this dose.

Note: CST = Clinical Study Team; DLT = dose-limiting toxicity; MTD = maximum tolerated dose.

The planned study drug doses for the dose escalation phase are summarized in Table 2. The starting dose for this study was 30 mg administered approximately every 12 hours, based on the results of GLP dose range-finding toxicology studies. Based on evaluation of the safety, tolerability, and PK/PD data of the previous dose levels, an intermediate dose level not specified in the tables below may also be explored. The MAD of AG-221 in this portion of the trial is 650 mg administered orally QD.

Confirmation of the primary malignancy is required. Subjects in the dose escalation phase are required to have IDH2 gene-mutated disease, documented by local site testing. Retrospective gene mutation analysis will be conducted at a central laboratory to support contemporaneous companion diagnostic development.

Table 2: Planned Dose Escalation Scheme

BID Schedule AG-221 Dose (mg)	QD Schedule AG-221 Dose (mg)
30 ¹	Not evaluated
50	50
75	75
100	100
150	150
Not evaluated	200
Not evaluated	300
Not evaluated	450
Not evaluated	650

¹ Starting dose.

The Clinical Study Team reviewed the emerging safety data from each cohort to determine if dose escalation should occur. If after the third subject completed the 28-day DLT evaluation period (ie, Cycle 1) no DLTs were observed, the study proceeded with dose escalation to the next cohort. If 1 of 3 subjects experienced a DLT during the first cycle, 3 additional subjects were enrolled in that cohort. If none of the additional 3 subjects experienced a DLT (ie, DLTs occurred in <2 of 6 subjects), dose escalation continued to the next cohort. If 2 or more subjects in a cohort experienced DLTs during the first cycle, dose escalation would be halted and the next lower dose level would be declared the MTD. Alternatively, an intermediate dose level between the non-tolerated dose level and the previously tolerated dose level might be explored and declared the MTD if <2 out of 6 subjects experienced a DLT at that dose. If the MTD cohort included only 3 subjects, an additional 3 subjects would be enrolled at that dose level to confirm that <2 of 6 subjects experience a DLT at that dose.

Note that if a given cohort initially enrolled 4 or 5 subjects (ie, if there were multiple subjects in the screening process at the time the third subject within a cohort began treatment), the same rules for dose escalation applied. If 1 of the 4 (or 5 subjects) experienced a DLT, the cohort would be expanded to include a total of 6 subjects; dose escalation would occur if only 1 of 6 subjects experienced a DLT and would be halted if 2 or more subjects experienced a DLT.

Increases in the dose of AG-221 for each cohort were guided by an accelerated titration design, where the daily dose could be doubled (100% increase) from one cohort to the next until National Cancer Institute Common Terminology Criteria for Adverse Events (NCI CTCAE) Grade 2 or greater AG-221-related toxicity was observed in any subject within the cohort. Following evaluation of the event(s) by the Clinical Study Team, subsequent increases in dose were guided by the observed toxicity, and potentially PK and PK/PD data until the MTD was determined. The absolute percent increase in the daily dose was determined by the Clinical Study Team, predicated on the type and severity of any toxicity seen in the prior dose cohorts (but never exceeded 100%).

The MTD was the highest dose that caused DLT in <2 of 6 subjects.

If no DLTs were identified during the dose escalation phase, dose escalation could continue for at least 2 dose levels above the projected maximum clinically effective exposure, as determined by an ongoing assessment of PK/PD and any observed clinical activity; this could occur in parallel with the expansion phase.

Subjects who did not meet any of the treatment withdrawal criteria could continue treatment beyond Cycle 1.

4.1.2. Overview of Phase 1/Part 1 Expansion

A dose of 100 mg QD has been selected for initial evaluation in Part 1 Expansion. Different dosing regimens may be explored within the expansion phase of the study if warranted based on the emerging clinical safety, PK, PD and clinical activity data. During the expansion phase, safety, PK/PD, and preliminary clinical activity data will be reviewed by the Clinical Study Team every 8 weeks.

Part 1 Expansion phase will enroll a minimum of 100 subjects that are divided into 4 nonrandomized arms of a minimum of 25 subjects per arm with IDH2-mutated hematologic malignancies as follows:

- Arm 1: R/R AML and age ≥ 60 years, or any subject with AML regardless of age who has relapsed following a bone marrow transplant (BMT).
- Arm 2: R/R AML and age < 60 years, excluding subjects with AML who have relapsed following a BMT.
- Arm 3: Untreated AML and age ≥ 60 years that declined standard of care chemotherapy.
- Arm 4: IDH2-mutated advanced hematologic malignancies not eligible for Arms 1 to 3.

As in the dose escalation phase, subjects in Part 1 Expansion are required to have IDH2 gene-mutated disease documented by local site testing with retrospective gene mutation analysis conducted at the central laboratory.

4.1.3. Overview of Phase 2

Based on continued ongoing demonstration of safety and clinical activity in the dose escalation portion of the study, the Phase 2 portion of the trial will further establish the clinical activity and safety profile of AG-221 in subjects with R/R AML with an IDH2 mutation.

The Phase 2 portion of the trial will enroll approximately 125 subjects with IDH2-mutated R/R AML defined as follows:

- Subjects who relapse after allogeneic transplantation.
- Subjects in second or later relapse.
- Subjects who are refractory to initial induction or re-induction treatment.
- Subjects who relapse within 1 year of initial treatment, excluding subjects with favorable-risk status according to National Comprehensive Cancer Network (NCCN)

Guidelines ([NCCN v1.2015](#)). Favorable-risk cytogenetics: inv(16), +(16;16), t(8;21), t(15;17).

The Phase 2 portion of the trial will be used to confirm the safety and clinical activity of AG-221 and to explore the relationship with PK/PD and IDH2 mutations for the treatment of subjects with R/R AML with an IDH2 mutation.

Subjects in the Phase 2 portion of the trial are required to have IDH2 mutation testing performed by a central laboratory in samples of bone marrow aspirate and peripheral blood, and confirmed positive in bone marrow aspirate and/or peripheral blood during screening prior to study treatment.

4.2. Study Endpoints

4.2.1. Efficacy Measures and Endpoints

Response to treatment will be assessed by the site Investigator, using a modification of the 2003 International Working Group (IWG) criteria for AML ([Cheson, et al. 2003](#)) ([Table 6](#) and [Table 7](#)). For subjects with malignancy type myelodysplastic syndromes (MDS), response to treatment will be assessed by the site Investigator using MDS modified IWG criteria ([Cheson, et al. 2006](#)) ([Table 8](#)).

Subjects who discontinue AG-221 treatment to receive a hematopoietic stem cell transplant (HSCT) will remain on study and be followed until documented disease progression or end of study.

Primary Endpoint:

Overall response rate (ORR): ORR is defined as the rate of complete response (CR), CR with incomplete neutrophil recovery (CR_i), CR with incomplete platelet recovery (CR_p), partial response (PR), and morphologic leukemia-free state (MLFS) for AML subjects and marrow CR (mCR) for MDS subjects.

Key Secondary Endpoints:

Complete response rate (CRR): CRR is defined as the rate of CR.

Rate of CR/CR_h: Rate of CR and CR_h where CR_h is defined as a response of bone marrow blast <5% with absolute neutrophil count (ANC) > 0.5x10⁹/L and platelet >50x10⁹/L.

Rate of complete response and complete response with incomplete hematological recovery (CR/CR_i/CR_p): Rate of CR, CR_i, and CR_p

Duration of response (DOR): Among subjects who have a response of CR, CR_i, CR_p, PR, or mCR (MLFS), DOR will be calculated from the date of the first occurrence of response to the date of documented disease relapse, progression or death, whichever is the earliest.

Overall survival (OS): Overall survival is defined as the time from first dose to the date of death.

56-Day transfusion independence (TI) rate: the rate of subjects who have been transfusion free for at least 56 consecutive days post baseline during treatment exposure period.

Other Secondary Endpoints:

Event-free survival (EFS): Event-free survival will be calculated from the date of first dose to the date of relapse, progression or death, whichever occurs first.

Duration of complete response (DOCR): Among subjects who have a best response of CR, DOCR will be calculated as the date of the first complete response to the date of documented disease relapse or death, whichever is earlier.

Duration of CR/CRh (DOCR/CRh): Among subjects who have a best response of CR or CRh, DOCR/CRh will be calculated as the date of the first CR or CRh to the date of documented disease relapse or death, whichever is earlier.

Time to response (TTR): Time to response will be assessed from the date of the first dose to the date of the first occurrence of any response, which includes CR, CRi, CRp, PR, and mCR/MLFS.

Time to Best Response (TTBR): Time to best response will be assessed from the date of the first dose to the date of the first occurrence of the best response.

Time to complete response (TTCR): Time to CR will be assessed from the date of the first dose to the date of the first CR.

Time to CR/CRh (TTCR/CRh): Time to CR/CRh will be assessed from the date of the first dose to the date of the first CR or CRh.

4.2.2. Safety Measures and Endpoints

Safety analyses will be performed separately for Phase 1 dose escalation, Part 1 expansion, the combined Phase 1, the Phase 2, and the combined Phase 1/2.

Safety will be evaluated by:

- Monitoring of adverse events (AEs), including determination of DLTs, serious adverse events (SAEs), and AEs leading to discontinuation. The severity of AEs will be assessed by the NCI CTCAE, version 4.03.
- Monitoring of safety laboratory parameters, physical examination findings, vital signs, 12-lead electrocardiograms (ECGs), evaluation of left ventricular ejection fraction (LVEF), and Eastern Cooperative Oncology Group (ECOG) performance status (PS).

4.2.3. Pharmacokinetic and Pharmacodynamics Measures and Endpoints

The endpoints in pharmacokinetics (PK) and pharmacodynamics (PD) analyses will be detailed in the separate PK/PD analysis plan.

4.3. Stratification, Randomization, and Blinding

This is an open label, single-arm study with no randomization and stratification.

4.4. Sample Size Determination

Phase 1:

Based on the planned dose escalation scheme, it is estimated that a minimum of 166 subjects were to be enrolled in the Phase 1 part.

Assuming that identification of the MTD/MAD requires the evaluation of 13 dose levels/schedules of AG-221 with up to 5 subjects per dose level (with the exception that the MTD requires 6 subjects), then 66 subjects will be enrolled during the dose escalation part of the study. Additional subjects may be needed for cohort expansion during dose escalation, for the replacement of subjects who are not evaluable for PK/PD, safety, clinical activity, or for evaluation of alternative dosing regimens other than the planned escalation scheme or the MTD, to optimize the RP2D and regimen(s).

Four cohorts of a minimum of 25 additional subjects in specific hematologic malignancy subsets (total a minimum of 100 subjects) will be enrolled in Part 1 Expansion of the study.

Phase 2:

The Phase 2 phase will enroll approximately 125 subjects with R/R AML with an IDH2 mutation. Additional subjects may be needed for the replacement of subjects who are not evaluable for PK/PD, safety, and/or clinical activity, or for evaluation of alternative dosing regimens.

5. GENERAL STATISTICAL CONSIDERATIONS

5.1. Reporting Conventions

Tabulations will be produced for subject disposition, demographic and baseline disease characteristics, safety, and clinical activity parameters. The study data will be analyzed and reported for efficacy/safety when applicable based on all subjects' data from the Phase 1 dose escalation, the Part 1 Expansion, the combined Phase 1, Phase 2, and the combined Phase 1/2 up to the data cut-off date of 29 July 2019.

Unless specified otherwise, the data will be presented as specified below:

1. In Phase 1 dose escalation, all subjects (combining different malignancy types [overall]) will be utilized. Data will be summarized by total daily dose groups, unless otherwise specified. The total daily dose is defined as the total dose a subject receives during a day based on the assigned or actual dose regimens for efficacy and safety, respectively.
2. In Part 1 Expansion, all subjects (combining different malignancy types) will be utilized and will be grouped into 4 arms (groups):
 - Arm 1: R/R AML and age ≥ 60 years, or any subject with AML regardless of age who has relapsed following a BMT.
 - Arm 2: R/R AML and age < 60 years, excluding subjects with AML who have relapsed following a BMT.
 - Arm 3: Untreated AML and age ≥ 60 years that decline standard of care chemotherapy.
 - Arm 4: IDH2-mutated advanced hematologic malignancies not eligible for Arms 1 to 3.
3. In the combined Phase 1, analyses will be presented by total daily dose groups as < 100 mg, 100 mg and > 100 mg for subjects with R/R AML. The overall subjects in the combined Phase 1 will be summarized by malignancy type including R/R AML, untreated AML, MDS, and other.
4. In Phase 2, data will be summarized primarily for all R/R AML subjects.
5. In the combined Phase 1/2, R/R AML will be presented by total daily dose groups as < 100 mg, 100 mg and > 100 mg, and the overall subjects will be presented by malignancy type.

For subjects who were discontinued from study treatment, underwent HSCT, and then re-started AG-221, data after restarting AG-221 will be excluded from all summary analyses except for death. The data collected after restarting AG-221 will be provided in listings.

Categorical variables will be summarized by frequency distributions (number and percentages of subjects) and continuous variables will be summarized by descriptive statistics (number of subjects, mean, standard deviation (SD), median, minimum, and maximum).

- Data from all study centers will be combined in the analysis.
- P-values will be rounded to 4 decimal places. P-values that round to 0.0000 will be presented as '<0.0001' and p-values that round to 1.000 will be presented as '>0.9999.'
- Confidence intervals (CIs) will be presented as 2-sided 95% CIs unless otherwise specified.
- Summary statistics will consist of the number and percentage of subjects in each category for discrete variables, and the sample size, mean, median, SD, minimum, and maximum for continuous variables.
- All percentages will be rounded to one decimal place. The number and percentage of responses will be presented in the form 'xx (xx.x)', where the percentage is in the parentheses.
- All analyses and summary tables will have the analysis population sample size for each treatment group in the column heading (ie, number of subjects).
- The day of the first dose of the study drug will be defined as study Day 1.
- For all analyses, unless noted otherwise, baseline will be defined as the most recent non-missing measurement by the first administration of study treatment. For subjects who receive the single dose on Day -3, baseline will be defined as the most recent measurement by the dosing on Day -3. For subjects who do not receive the single dose on Day -3, baseline will be defined as the most recent non-missing measurement by the first dose date.
- To summarize efficacy/safety data by visit, the post-baseline results will be summarized by the scheduled visit as appropriate.
- Calculation of Cycles:
 - The start date of each cycle will be determined based on scheduled study visit date for each subject, except for Cycle 1 which will use the first dose date of study drug as starting day. Once the start dates, eg, $S_1, S_2, S_3 \dots$ are determined, the end date of each cycle is calculated as the one day before the start date of the following cycle, ie, $E_i = S_{i+1} - 1$. The cycle number for each date of interest, eg, AE or study medication will be calculated based on event start date and the cycle window start and end dates. If an event date is on or after S_i and before S_{i+1} , the corresponding cycle number will be i . For the last cycle, the end date will be the last dose date, unless otherwise specified.

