Subjects who discontinue from study treatment and undergo HSCT will enter HSCT follow-up and are to be evaluated on study until relapse or end of study. Subjects who relapsed after HSCT may be eligible to restart treatment with AG-221 with Medical Monitor approval and at the discretion of the Investigator, if they have confirmed recurrent IDH2 mutant positive disease, no cancer treatment was administered since the last dose of AG-221 (with the exception of anti-neoplastic therapies used in the course of HSCT such as conditioning regimen or induction-type regimen and anti-GVHD prophylaxis [i.e., methotrexate]), the subject meets the safety parameters listed in the Inclusion/Exclusion criteria, and the trial is open. Subjects will resume AG-221 therapy at the same dose and schedule at the time of discontinuation. These subjects will 're-enter' the study at Cycle 3 and have assessments conducted per that visit and beyond.

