9. STUDY TREATMENTS AND EXTENT OF EXPOSURE

Descriptive statistics will be used to summarize treatment duration, duration of treatment exposure, cumulative dose, average daily dose, dose intensity, relative dose intensity and dose modification. These analyses will be presented by subject groups as described in items 1 to 5 of [Section 5.1](#) for the SAS. Tables will also be provided for Phase 1 dose escalation by assigned dose groups in the DDS.

Cycle duration is defined as the period from Day 1 of each cycle to one day prior to the Day 1 of the subsequent cycle; for the last cycle, the end date is the date of last dose.

For subjects who discontinued from study treatment but restarted AG-221, the data after restarting AG-221 will not be used for analysis in this section, however, will be presented separately in listings.

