9.1. Treatment Duration and Exposure

Duration of treatment (months) is defined as: $(\text{treatment end date} - \text{treatment start date} + 1) / 30.4$. The treatment start date is the date of the first dose of study drug, and the treatment end date is the last dose date. For subjects who are still on treatment at a data cut-off date, treatment end date will be the earlier date of data cut-off date and last day that the subjects take study drug.

Duration of treatment exposure (months) is defined as: $(\text{Treatment end date} - \text{treatment start date} + 28) / 30.4$. If death date is after treatment end date and earlier than 28 days after treatment end date, duration of treatment exposure is defined as: $(\text{Death date} - \text{treatment start date} + 1) / 30.4$.

Treatment duration and exposure will be summarized by investigator assessed best response for the combined Phase 1, Phase 2, and the combined Phase 1/2 R/R AML subjects and overall.

A subject data listing of study drug records will be provided.

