11.1. Adverse Events

Adverse events will be analyzed in terms of treatment-emergent adverse events (TEAEs), which are defined as any AEs that begin or worsen on or after the start of study drug through 28 days after the last dose of study drug. All AEs will be coded using MedDRA version 20.0. The severity will be graded based on NCI CTCAE version 4.03.

A treatment-related TEAE is defined as TEAE that is suspected (possibly or probably related) by the Investigator to be related to the study drug. The incidence of TEAEs will be summarized by MedDRA SOC and PT. The intensity of AEs will be graded 1 to 5 according to the NCI CTCAE version 4.03. For all other AEs not described in the CTCAE criteria, the intensity will be assessed by the Investigator as mild (Grade 1), moderate (Grade 2), severe (Grade 3), life-threatening (Grade 4) or death (Grade 5). The Grade 3-4 TEAEs will also be summarized by MedDRA SOC and PT. If a subject experiences the same AE more than once with different toxicity grade, then the event with the highest grade will be tabulated in “by grade” tables. If a subject experiences multiple AEs under the same PT (SOC), then the subject will be counted only once for that PT (SOC).

Analysis of TEAEs of special interest will be presented for combined Phase 1, Phase 2 and the combined Phase 1/2 as described in items 3 to 5 of [Section 5.1](#). Some special interested PTs will be grouped and the TEAEs will be summarized by Grouped Terms and be presented for combined Phase 1/2 as described in item 5 of [Section 5.1](#).

The number of subjects with at least one TEAE will be summarized. Analysis for all TEAEs and Grade 3-4 TEAEs by descending frequency of PT will also be summarized. Tabulations of overall summary of TEAEs, all TEAEs by SOC/PT and Grade 3-4 TEAEs will be summarized by cycles for combined Phase 1, Phase 2, and the combined Phase 1/2. All TEAEs and Treatment-related TEAEs leading to study drug discontinuation, reduction or interruption will be summarized separately. Tables summarizing the incidence of TEAEs will be generated for each of the followings:

1. Overall summary of TEAEs.
2. All TEAEs by SOC and PT.
3. Treatment-related TEAEs by SOC and PT.
4. All TEAEs by descending frequency of PT in total column.
5. All TEAEs with Grade 3-4 by SOC and PT.
6. TEAEs by maximum severity.
7. Treatment-related Grade 3-4 TEAEs by SOC and PT.
8. All TEAE with Grade 3-4 by descending frequency of PT in total column.

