11.3. Death

Cause of death will be summarized in the SAS with the following categories: on-treatment death, post-treatment death, and overall.

1. All deaths within 28 days of the last dose of study drug.
2. All deaths after 28 days of the last dose of study drug.
3. All deaths.

The 30-day and 60-day death rate will be summarized for all deaths. Death analysis will be summarized for the combined Phase 1, Phase 2 and the combined Phase 1/2 as described in items 3 to 5 of [Section 5.1](#).

A death listing will include deaths for all screened subjects during pre-treatment, on-treatment, and post-treatment periods.

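### Safety data after a post-transplant restart of AG-221 are left out of every summary except deaths, and the on-/post-treatment death split is undefined for those subjects

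*SAP*

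**What the plan says.** Re-treatment is part of the planned study. Protocol 10.1 allows subjects who relapse after HSCT to restart, subject to conditions and Medical Monitor approval: "Subjects will resume AG-221 therapy at the same dose and schedule at the time of discontinuation". They re-enter at the Cycle 3 visit and follow the assessment schedule from there, so safety data on the second course are collected.

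SAP 5.1 then sets a general rule for these subjects: "data after restarting AG-221 will be excluded from all summary analyses except for death". It adds: "The data collected after restarting AG-221 will be provided in listings". SAP 9 repeats the rule for exposure: "the data after restarting AG-221 will not be used for analysis in this section, however, will be presented separately in listings".

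Three definitions depend on a last dose:

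- SAP 9.1, treatment duration: "the treatment end date is the last dose date".
- SAP 11.1, the TEAE window: "any AEs that begin or worsen on or after the start of study drug through 28 days after the last dose of study drug".
- SAP 11.3, on-treatment death: "All deaths within 28 days of the last dose of study drug". Later deaths form the post-treatment category.

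None of the three says which course is meant when a subject has had two. SAP 11.1 also plans a dedicated listing of adverse events in re-enrolled subjects. The Safety Analysis Set (SAP 5.2.2) takes in everyone who received at least one dose and makes no exception for re-treatment.

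**The concern.** There is a plain efficacy reason to stop at restart: transplant intervenes, and a response on the second course cannot be separated from it. The SAP applies the same cut to safety without giving a reason. A subject on a second course is taking the study drug, and toxicity there is on-drug toxicity. A listing preserves the records but gives no rate and no time at risk.

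The loss is sharpest for fatal events. A non-fatal event on re-treatment may repeat a preferred term already counted in the first course, and then incidence does not change. Anyone who restarted survived the first course, so a fatal adverse event on re-treatment is always new and always missing from the fatal-TEAE tables (items 18 and 19 in SAP 11.1). The death itself stays in the SAP 11.3 table, leaving a death with no matching event.

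The special-interest comparisons are exposed too. SAP 11.2 compares subjects with and without differentiation syndrome. A subject whose only episode came on re-treatment would be placed in the group without it.

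**Working it through.** The plan states no figure for this point, so there is none to reproduce. The check sets the rules side by side and adds simple arithmetic for size.

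**Step 1: what the exclusion reaches.** SAP 5.1 covers all summary analyses and exempts only death. The summaries of TEAEs, serious TEAEs, special-interest events, laboratory values, ECG, vital signs, LVEF and ECOG status all fall under it. Exposure is removed again by SAP 9. What remains is listings, plus the death tables.

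**Step 2: the last dose under two readings.** Take an invented subject: last first-course dose on Day 100, HSCT on Day 120, restart on Day 310, fatal drug-related event and death on Day 325, still dosing.

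| Item | Last dose = Day 100 | Last dose = final restart dose |
|---|---|---|
| Days from last dose to death | 325 − 100 = 225 | 0 |
| SAP 11.3 class | post-treatment (225 > 28) | on-treatment |
| TEAE window ends | Day 100 + 28 = Day 128 | 28 days after the restart dose, cut by the death |
| Fatal event in the fatal-TEAE tables | no: outside the window, and excluded by SAP 5.1 | no: inside the window, but excluded by SAP 5.1 |
| Restart exposure in SAP 9 | none | none |

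The fatal event is absent from the TEAE tables under both readings. Only the class of the death changes.

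The second reading has a further side effect. SAP 5.1 excludes data after restart, not data between the courses. The off-drug interval from Day 129 to Day 309 (309 − 129 + 1 = 181 days) would then count as treatment-emergent, while the on-drug days from Day 310 would be dropped.

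**Step 3: is the gap between courses usually longer than 28 days?** Restart comes after transplant and then relapse, and the relapse footnote to SAP Table 6 asks for two consecutive assessments at least a month apart. So with the pre-HSCT dose as reference, a re-treatment death would normally be post-treatment.

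**Step 4: size.** The number of restarts is not given. If *k* re-treated subjects each have an event not already counted, the shift is *k*/*N*:

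| *k* (assumed) | Phase 2, *N* = 125 | Planned total, *N* = 291 |
|---|---|---|
| 1 | 0.8 points | 0.3 points |
| 5 | 4.0 points | 1.7 points |
| 10 | 8.0 points | 3.4 points |

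As a guide to plausible *k*, assume that 10% of 125 go to HSCT (12.5) and that 10% to 30% of those restart: 12.5 × 0.10 = 1.25 to 12.5 × 0.30 = 3.75, or about 1 to 4 subjects. Both percentages are assumptions. They give a count of restarts, not of events.

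**The case against.** The strongest defence is that keeping re-treatment out of the main tables is sound. SAP 5.1 fixes baseline before the first dose and counts cycles from it. Re-treated subjects come after transplant, possibly with conditioning and GVHD prophylaxis, and re-enter at Cycle 3. Pooling them would mix transplant effects into by-cycle and change-from-baseline summaries. This stands, and it argues for a separate table rather than pooling. It does not argue for having no summary.

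The data are also not hidden. They are listed, with a dedicated listing for re-enrolled subjects, and the deaths remain in both the all-deaths category and overall survival. This stands as well, though listings give no incidence or exposure.

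A reader might infer that the SAP classes an on-drug re-treatment death as post-treatment. The documents do not say so. SAP 11.3 names no course, SAP 5.1 exempts death from the exclusion, and SAP 9 confines its exclusion to its own section. Read literally, the final restart dose is the last dose and the death is on-treatment. The supportable statement is that the class is undefined.

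A reader might also infer that the death table and the fatal-TEAE tables can never agree. They measure different things and would differ in any case, since SAP 11.3 includes deaths more than 28 days after dosing. The exclusion adds an unexplained gap only if a re-treated subject has a fatal adverse event, and the documents report no such case.

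Finally, protocol 10.6.5 and 12.5.4 are redacted, so whether the protocol handles re-treatment events differently cannot be checked.

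**Conclusion.** The concern holds in a limited form. By a stated rule, on-drug toxicity during planned re-treatment receives no incidence, denominator or exposure in any summary, and a fatal event there would drop out of the fatal-TEAE tables while its death is counted. Separately, the on-/post-treatment split is undefined for re-treated subjects: on-treatment by the final restart dose, normally post-treatment by the pre-HSCT dose.

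The size is probably small and cannot be fixed from the documents. Each additional affected subject moves a Phase 2 rate by 0.8 points, and the range of about 1 to 4 restarts rests on assumed percentages. Under-reporting is possible rather than shown, because an event that repeats a first-course preferred term changes nothing. The consequence is mainly for rare or fatal events, where one case can be the whole signal. The primary response rate is untouched. The change is worth making before the tables are produced, since it needs no new data.

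**What to change.** 1. Keep the SAP 5.1 exclusion for efficacy and for the first-course safety tables, and say that this is its scope.
2. Add one re-treatment-period safety table: TEAEs, serious TEAEs, special-interest events and fatal TEAEs from restart to 28 days after the last restart dose. Use the number of re-treated subjects as denominator and report their restart exposure. Amend SAP 9 to allow that exposure summary.
3. In SAP 11.1 and 11.3, define the last dose by course. End the first-course TEAE window 28 days after the last pre-HSCT dose, so that the later off-drug interval does not count as treatment-emergent.
4. In SAP 11.3, either classify deaths by the most recent AG-221 dose in either course or give re-treatment deaths their own row.

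The cost is some SAP wording and one small table built from data already collected and listed. Reported toxicity may look slightly worse, and with few re-treated subjects the table will be descriptive only.
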